**NCT number (if available) : Not applicable**

**Date of the document: June 1, 2024**

This study aims to assess the effect of implementing nursing interventions on preventing medical device-related pressure injuries in critically ill patients.

Operational definition: The selected nursing interventions refer to the skin care Bundle, which includes eight key components.

Design and methods:

Research design: A parallel randomized control trial research design will be conducted.

Setting: The current study was conducted in intensive care units (ICUs) at Main Alexandria University Hospital in Egypt. Those units received patients with critical illness and immobility who were independent on nursing care to meet their basic needs.

Subjects:

This study will include a convenience sample of 120 critically ill patients who require ventilatory support. Adult patients (age  $\geq 18$  years) in the ICU who were more than 24 hours after admission were eligible for inclusion. The exclusion criteria for the patients were as follows: (i) patients who had skin diseases such as systemic lupus erythematosus and burns that may have influenced the judgment of medical device related pressure injury; (ii) patients who were not in the ICU for treatment or examination during the investigation; and (iii) patients with medical device related pressure injury before they were admitted to the ICU

Tools of the study:

Three parts make up Tool one, which evaluates general patient data.

Part one: Patients' characteristics such as age, sex, admission cause, history, length of stay, APACHE II score, body mass index, no of invasive devices used and mechanical ventilator duration.

Part two: Patient clinical assessment includes vital signs such as oxygen saturation, albumin, type of nutritional support, level of consciousness, capillary refill, and edema grade.

Part three: skin assessment. The Braden Scale for Predicting Pressure Sore Risk is defined as a pressure ulcer development risk prediction score that is based on a patient's sensory perception, skin moisture levels, activity, mobility, nutrition, friction, and shearing. Scores range from 6 to 23. A score of 15–18 indicates that the patient is at mild risk for developing a pressure ulcer; a score of 13–14 indicates moderate risk; a score of 10–12 indicates high risk; and a score of equal to or less than 9 indicates severe risk.

Two medical devices are used and consist of three parts.

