Part one: ICU medical device assessment: this part is used to assess the number of non-invasive and invasive devices and whether they are needed or not. Each site will be assessed for the Pressure Ulcer Staging Form based on classification of Pressure Ulcer Grading:

Grade 1: non-blanchable erythema of intact skin. Discoloration of the skin, warmth, oedema, induration, or hardness may also be used as indicators, particularly in individuals with darker skin.

Grade 2: Partial thickness skin loss involving the epidermis, dermis, or both. The superficial ulcer presents clinically as an abrasion or blister.

Grade 3: Full-thickness skin loss involving damage to or necrosis of subcutaneous tissue that may extend down to, but not through, underlying fascia.

Grade 4: Extensive destruction, tissue necrosis, or damage to muscle, bone, or supporting structures with or without full thickness skin loss

Two medical devices are used and consist of three parts.

Method:

Ethical approval will be obtained from the university committee.

After an explanation of the study's purpose, hospitals administrative authorities' permission to perform the study was acquired from selected hospitals.

The reliability of the tool was established, and it was accepted. A pilot study was done on 10% of the studied population to assess the accessibility of two tools, and necessary modifications were made.

Data collection phase:

A letter was submitted from the Dean of the Faculty of Nursing, Damanhur University, to the director of intensive care units at the Alexandria main university in Alexandria government hospitals in Egypt.

The validity of the instruments was verified by presenting them to five experts in the field of the study, who revised them. The recommended modifications will be made.

On the first admission day, the researchers assessed all newly admitted mechanically ventilated patients to identify the exclusion criteria. They were assigned equally to controlled and intervention groups.

The patients will be assigned to two equal groups: the control (A) and intervention (B) groups.

Group A received routine nursing care for medical devices.

The intervention group (B) received skin care bundle. It includes eight key components:

Secure devices and protect the skin with dressings in high-risk areas.

K: Keep repositioning more frequently than twice daily (if not medically contraindicated); remove the medical device as soon as medically feasible.

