Inspect the skin under the device more than twice daily; high-risk patients will require more frequent assessments.

Nutrition and hydration, nutrition deprivation, and insufficient dietary intake are risk factors for medical device-related pressure injuries and impaired wound healing.

Choose the correct size and type of medical device to fit the individual.

A. Avoid placing devices over sites of prior or existing pressure injury or assess the patient's risk status.

Report medical device-related pressure injuries correctly and immediately; monitor incidence and prevalence.

Educate staff on the correct use of devices and prevention of skin breakdown (younger and older patients are at high risk); never apply additional pressure when securing a device; and do not position the patient directly on a medical device unless it cannot be avoided.

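### Several ICUs take part, but the protocol fixes allocation balance only for the two groups overall and does not list ICU as a data item; balancing within ICU would be a cheap, modest gain in precision

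*Protocol*

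**What the plan says.** Four statements in the protocol bear on this.

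- Type of trial, as named under the design heading: "A parallel randomized control trial research design will be conducted".
- Place, as named in the Setting paragraph: "The current study was conducted in intensive care units (ICUs) at Main Alexandria University Hospital in Egypt". Units are plural; their number is not given.
- Sample, as named in the Subjects paragraph: "This study will include a convenience sample of 120 critically ill patients who require ventilatory support".
- Allocation, in the Data collection phase: "They were assigned equally to controlled and intervention groups", and again "The patients will be assigned to two equal groups: the control (A) and intervention (B) groups". Both sentences concern the groups as a whole. Neither mentions ICU, strata or blocks.

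The comparator is described in one line: "Group A received routine nursing care for medical devices". Tool one Part one gives examples of the patient characteristics to be recorded (age, sex, APACHE II score, number of invasive devices and others). ICU is not among them. The list is illustrative, so it does not rule out recording ICU, but it does not require it.

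**The concern.** The ICU is a plausible prognostic factor here. The outcome depends on device use, case mix and nursing practice, all of which can vary between units even within one hospital. With only 60 patients per group and balance fixed only overall, one group can by chance draw more patients from a higher-risk unit. That adds variation to the estimated effect which allocation within ICU would remove.

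The data item matters as much as the allocation rule. If ICU is not recorded, no later analysis can adjust for it, and readers cannot be shown how the groups split across units. Both are matters for the protocol, because a SAP cannot restore balance or recover a field that was never collected.

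**Working it through.** **The protocol's own figure.** 120 patients in two equal groups gives 120/2 = 60 per group. The protocol states no event rate, effect size, alpha or power, so nothing further can be reproduced.

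**Assumptions (not in the protocol).** *k* equal-sized ICUs, *k* = 2, 3, 4 or 6; unit injury risks evenly spaced from 15% to 45% (mean 30%); no bundle effect; 60:60 random allocation without regard to ICU.

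**Formulas.** Let *D* be the difference between groups in mean expected risk that arises from ICU mix alone, and σ² the variance of the unit risks. Drawing 60 of 120 patients without replacement gives mean(*D*) = 0 and

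Var(*D*) = 4σ²/119.

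The remaining binomial variance of the group difference is

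*W* = (0.30 × 0.70 − σ²) × (1/60 + 1/60) = (0.21 − σ²)/30.

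Allocation 1:1 within each ICU makes *D* = 0 and leaves only *W*.

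**Example with 4 ICUs** (risks 15, 25, 35 and 45%):

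- σ² = 2 × (0.15² + 0.05²)/4 = 0.0125
- Var(*D*) = 4 × 0.0125/119 = 0.00042, so SD(*D*) is 2.0 points
- *W* = 0.1975/30 = 0.00658, SD 8.1 points
- Total = 0.00700, SD 8.4 points; share due to ICU mix = 0.00042/0.00700 = 6.0%

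**All cases.** The 95% limit for |*D*| and the type I error (pooled two-sided z-test at 0.05, ignoring ICU) come from 200,000 simulated allocations each.

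| ICUs | σ² | SD(*D*), points | 95% limit of abs. *D*, points | Share of variance | SD, overall allocation | SD, within ICU | Type I error, overall allocation |
|---|---|---|---|---|---|---|---|
| 2 | 0.0225 | 2.7 | 5.0 | 10.8% | 8.4 | 7.9 | 0.053 |
| 3 | 0.0150 | 2.2 | 4.5 | 7.2% | 8.4 | 8.1 | 0.052 |
| 4 | 0.0125 | 2.0 | 4.0 | 6.0% | 8.4 | 8.1 | 0.053 |
| 6 | 0.0105 | 1.9 | 3.6 | 5.0% | 8.4 | 8.2 | 0.052 |

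The simulated mean of *D* is 0.000 in every row. Perfect balance by ICU would lower the SD of the group difference by about 2.5% (6 ICUs) to 5.5% (2 ICUs).

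**Sensitivity to the assumed risks.** With 2 to 4 ICUs and other spreads, from 20% versus 40% to 10% versus 50%, the 95% limit is 3.3–6.7 points and the type I error 0.051–0.054. If the 4 unit risks ran only from 25% to 35%, a third of the assumed range, the limit would fall to about 4.0/3 = 1.3 points and the variance share to about 6.0%/9 = 0.7%.

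**How uneven a single ICU can become.** The chance that at least one ICU is split 60:40 or worse is about 4%, 36%, 67% and 96% for 2, 3, 4 and 6 ICUs. The last figure looks alarming but means 12 versus 8 patients. A split of 80:20 or worse has a chance near 0% with 2 or 3 ICUs, 0.1% with 4 and 3.5% with 6.

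**The case against.** The strongest reply is that unstratified individual randomisation is a valid design. Chance imbalance by unit is part of the random error that the ordinary test and confidence interval already cover, and the simulated type I error bears this out. The gain from stratifying is a few per cent of the standard deviation, and it rests on assumed figures. All of this stands, and it limits the point to a refinement.

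It can also be said that the text does not exclude balance within ICU, and that stratification details often sit in a SAP. The first is true: two equal groups overall is compatible with equal groups in each unit. The protocol simply does not provide for it. The second holds for the analysis, but not for the allocation rule or the collected fields.

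Three stronger readings are tempting and are not supported.

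- *Differences between units could pass for a bundle effect.* Under the stated randomised design they add noise and no systematic shift.
- *The control is each unit's own routine care.* The protocol says only that routine care was given; it does not say that this care differs by unit.
- *Whole ICUs form the groups.* A reader might infer this because one bundle component acts on staff: "Educate staff on the correct use of devices and prevention of skin breakdown". Confounding would then be serious. In simulations with two unit-risk levels from 20%/40% to 10%/50%, or four risks from 10% to 40%, the type I error was 0.26–0.35 with 4 ICUs and 0.68–0.999 with 2. But the protocol speaks of patients being assigned and nowhere states allocation by unit.

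**Conclusion.** The point holds as a minor matter of precision. Several ICUs take part, the only balance fixed is two equal groups overall, and ICU is not a named data item. Given individual randomisation as stated, the consequence is chance imbalance in ICU mix: within about 3.6 to 5 percentage points in 95% of allocations, and about 5–11% of the variance of the group difference. There is no systematic bias, and the type I error stays near 5%. The size depends on the assumed 2 to 6 equal ICUs and risks of 15–45%; with smaller differences between units it shrinks quickly. The conclusion that there is no bias depends on assignment being truly random. The protocol calls the trial randomised but does not describe the method, so a split of the groups by ICU would also be a useful check. Priority: optional.

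**What to change.** In the Data collection phase, state that patients are assigned 1:1 within each ICU, in randomly permuted blocks of varying size. Add ICU to Tool one Part one. Compare the groups with ICU as a stratum; under the assumptions above, a test that ignores ICU after allocation within ICU is slightly conservative (simulated type I error 0.040–0.046), so the stratum is needed to gain the precision.

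The protocol mixes past and future tense, so assignment may already be complete. In that case, record ICU for every patient, report the group split by ICU and stratify the comparison by ICU.

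The cost is one allocation list per ICU instead of one overall, and one extra field. The drawback is that assignments near the end of a block may be guessed, which varying block sizes limit but do not remove.
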